7.2 Consent

In many cluster randomized comparative effectiveness trials, a waiver of consent is obtained from the IRB of Record. The rationale for the waiver of consent is that all patients will receive treatments that are effective and within standards of care, they will receive one of the study treatments as part of their routine care regardless of study participation, the data collection is minimal and obtained from the patient's medical records, the trial involves no more than minimal risk to the patient, and that the waiver of consent will not adversely affect the rights and welfare of the patient. Most of these concepts apply to the current trial, as the PREPARE trial is comparative effectiveness research where patients will receive one of the preoperative antiseptic skin solutions regardless of their participation in the study. Additionally, patients are never included in the decision-making process for the choice of antiseptic preparation solution, and, in most situations, they are not even aware of which solution is used. However, in contrast to many cluster randomized crossover trials, PREPARE trial personnel will need to contact participants directly to collect baseline and outcome data, as this information cannot be reliably obtained from the patients' medical records. Therefore, study personnel will obtain informed consent from patients prior to data collection. This consent process will allow study participants to be informed about the study rationale and provide consent for ongoing surveillance and data collection.

To increase enrollment and to avoid missing potential study participants, the consent process may take place up to 3 weeks post-fracture for open fracture patients and up to 6 weeks post-fracture for closed fracture patients. Consultation during the study design phase with IRB members and patient advisors confirmed the acceptability of this flexible approach, where consent may be obtained after the intervention. The primary rationale for allowing consent after the intervention is

consistent with the waiver of consent principles outlined above, but in addition, the patient and IRB stakeholders recognized that obtaining consent prior to the patient's first surgery could add undue decision making stress to a patient who is awaiting surgical management of a serious extremity injury; allowing consent after their surgery would likely facilitate an improved consent process.

The consent process will typically take place in the patient's hospital room or in the outpatient fracture clinic, either before or after the patient has had surgery(ies) to manage their fracture. If the patient is unable to provide informed consent (e.g., due to their injury, language restrictions) within 3 weeks of their open fracture or 6 weeks of their closed fracture, informed consent will be obtained from their proxy. In addition, if a patient has been discharged from hospital prior to being invited to participate in the study, a delegated member of the clinical care team may initiate the consent process by telephone, as approved by the IRB of Record.

To obtain informed consent, delegated study personnel should follow the below procedures:

- Present study information in a manner that is understandable to the potential participant/proxy.
- Discuss the study with the potential participant/proxy and answer any questions he or she asks.
- Allow the potential participant/proxy an opportunity to discuss participation with their family, friends, or family physician, if desired.
- Confirm that the participant/proxy understands the risks and benefits of participating in the study and that their participation is voluntary.
- Complete and obtain signatures for informed consent form and obtain contact information from the participant/proxy.
- Provide/send the participant/proxy with a paper/electronic copy of the signed consent form.

Consent may be obtained electronically or using pen and paper consent forms, as approved by the IRB of Record. If potential participants are contacted by telephone, documenting written informed consent will involve the following procedures:

- The study team confirms the potential participant's interest in learning more about the study and verifies the mailing address or fax number to which the consent form can be sent.
- A blank consent form is mailed or faxed along with a cover letter that introduces the study and explains when the phone conversation will occur. A stamped, self-addressed envelope is provided if standard mail is used so the participant can return the signed consent document to the study team.
- After the potential participant has received the document, a member of the study team calls the participant and walks through the entire document over the phone, answering questions and making notes about the participant's questions. Time and date of the conversation should be recorded.
- Once all questions are answered, the participant signs the consent form if they are willing to participate. S/he returns the consent form by mail or fax.
- Once received, the study team member who conducted the consent conversation should sign the consent form and date with today's date. To explain the discrepancy, this individual should also write a note on the consent form stating that the participant's consent was obtained by phone on xx date (the date the participant signed.)

- The participant should receive back a fully-signed copy of the consent form for their records.

The process of obtaining and documenting informed consent will be completed in accordance with local Good Clinical Practice recommendations. Consent procedures and forms, and the communication, transmission and storage of patient data will comply with the IRB of Record requirements for compliance with The Health Insurance Portability and Accountability Act.

Upon providing informed consent, study participants will be followed for 12 months from their fracture. Given the short follow-up time, the need for a regular reassessment of consent will not apply; however, participants may withdraw their consent at any time.

7.3 Confidentiality

Information about study participants will be kept confidential and will be managed in accordance with the below rules:

- All study-related information will be stored securely.
- All study participant information will be stored in locked file cabinets, or locked room, as applicable, and accessible only to study personnel.
- All paper and electronic CRFs will be identified only by a coded participant number.
- All databases will be password protected.

In the event that a participant revokes authorization to collect or use personal health information, the clinical site retains the ability to use all information collected prior to the revocation of participant authorization. For participants who have revoked authorization to collect or use personal health information, attempts should be made to obtain permission to collect at least vital status (i.e., primary outcome data) at the end of their scheduled study period.

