4.8 Outcome Measures

4.8.1 Primary Outcome

The primary outcome is SSI, guided by the CDC's National Healthcare Safety Network reporting criteria (2017),²⁵ which includes superficial incisional SSI within 30 days and deep incisional or organ/space SSI within 90 days of fracture surgery (Table 3). Since the management of some fractures may have more than one operative procedure as part of an intentionally staged surgical plan (e.g., multiple irrigation and debridements, wound closures, temporary stabilization surgeries, definitive fixation surgery), the primary outcome will include any SSI event from the date of fracture to the end of the 30- and 90-day post-operative surveillance periods from their definitive fracture management surgery. For participants with multiple fracture regions, the date of the definitive fracture management surgery will be matched to the fracture region with the SSI.

Table 3: CDC Surgical Site Infection Criteria

Outcome	Description
Superficial Incisional SSI	
Date of event for infection occurs from the date of fracture to 30 days after the definitive fracture management surgery (where day 1 = the procedure date)
 
AND
 
involves only skin and subcutaneous tissue of the incision
 
AND
 
patient has at least one of the following:
 
 a. purulent drainage from the superficial incision. b. organisms identified from an aseptically-obtained specimen from the superficial incision or subcutaneous tissue by a culture or non-culture based microbiologic testing method which is performed for purposes of clinical diagnosis or treatment (e.g., not Active Surveillance Culture/Testing [ASC/AST]). c. superficial incision that is deliberately opened by a surgeon, attending physician or other designee and culture or non-culture based testing is not performed. 
AND

Outcome	Description

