#### 119 **4.3 Participant Withdrawal**

120 The level of withdrawal will be tabulated and classified as “withdrawal of consent” or “lost to  
121 follow-up”. Participant deaths will also be tabulated.

122

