181 estimates presented as odds ratios with 95% confidence intervals as recommended. For patients  
182 with multiple closed fractures, the patient will remain the unit of analysis regardless of whether  
183 the study event occurs in one or more of their closed fractures. As suggested by Morgan et al. and  
184 Hemming et al., we will include time and treatment as fixed effects and use random effects to  
185 account for the complex correlation structure. We will consider three correlation structures, in  
186 the following sequence: exponential decay, nested exchangeable, and exchangeable. If we  
187 experience convergence issues or find insufficient between-period correlation to support an  
188 exponential decay or nested exchangeable structure, we will assume an exchangeable correlation  
189 structure. If we encounter convergence issues even with this model, a more simplified structure  
190 will be considered. The models will also include prespecified covariates prognostic of infection or  
191 unplanned reoperation as fixed effects, which includes the presence or absence of a severe soft

192 tissue injury and the presence or absence of a periarticular fracture. The same covariates will be  
193 used for all primary and secondary outcomes. This planned analysis is a more complex structure  
194 than we proposed in the initial study protocol but represents the most recently recommended  
195 statistical techniques for cluster-crossover trial analysis. Estimated within-period  
196 intracluster correlation coefficients will also be reported.

197

198 Our primary and secondary analyses will use multiple imputations to account for missing data.  
199 The multiple imputation analysis will create 100 imputed datasets using multivariate imputation  
200 by chained equations and pooled using Rubin's rules for combining. The imputation will be  
201 performed separately within each treatment arm.

202

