262 intervention received at their definitive fracture management surgery. Participants who do not  
263 receive one of the study interventions will be removed from this analysis. Similar to the primary  
264 analysis, we will use mixed effects regression models with a binomial distribution and the same  
265 covariates and correlation structure as the primary model. A more simplified structure will be  
266 considered if we encounter convergence issues with this model.

267

268 *Missing Data:* While we anticipate minimal missing outcome data, we will perform a sensitivity  
269 analysis on the primary and secondary analyses to explore the impact of missing outcome data.  
270 Our sensitivity analysis will be a complete case analysis, including only those patients with a  
271 known status of the outcome being analyzed.

272

273 *Bayesian Analysis:* The Bayesian analyses will be performed using four different priors (neutral  
274 with moderate strength, neutral flat, optimistic with moderate strength, and pessimistic with  
275 moderate strength) defined on a log-odds scale and described below. The neutral priors will be  
276 centered on a log odds of 0 (odds ratio of 1). The neutral flat prior will have a standard deviation  
277 of 100. The optimistic prior will be centered on the estimated effect size of a 0.64 odds ratio (log  
278 odds of -0.45). In contrast, the pessimistic prior is centered on the same effect size but for the  
279 alternative treatment. As suggested by Zampieri et al., the standard deviation of 0.44 was selected  
280 for the moderate strength priors as it allows for a 15% probability of the alternative treatment  
281 benefit in both the optimistic and pessimistic prior. The prior probability of our neutral prior with  
282 a moderate strength distribution implies a 68% chance the estimated effect will be between an odds

[figure not shown]
[figure not shown]
283 ratio of 0.64 and 1.36. The neutral prior with moderate strength will be our preferred prior in this  
 284 sensitivity analysis.

[figure not shown]
285

286 The modeling for the Bayesian analysis will be consistent with our primary analysis. We will use  
 287 a mixed effects regression model with a Bernoulli distribution. The model will include time and  
 288 treatment as fixed effects and use random effects to account for the complex correlation structure.  

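### Protocol 7.3 labels vital status as the primary outcome, so a site can follow the rule for revoked authorization without asking about SSI or reoperation

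*Protocol*

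**What the plan says.** Protocol 7.3 (Confidentiality) covers participants who revoke authorization to collect or use personal health information. It makes two statements. First, "the clinical site retains the ability to use all information collected prior to the revocation of participant authorization". Second, for data after that point, "attempts should be made to obtain permission to collect at least vital status (i.e., primary outcome data) at the end of their scheduled study period".

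Protocol 4.8.1 defines the outcome differently: "The primary outcome is SSI", counted as "superficial incisional SSI within 30 days and deep incisional or organ/space SSI within 90 days of fracture surgery". The same section then ties both windows to the definitive fracture management surgery. Protocol 4.8.2 makes unplanned fracture-related reoperation within 12 months of fracture the secondary outcome. On the length of the study period, Protocol 7.2 says: "Upon providing informed consent, study participants will be followed for 12 months from their fracture".

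Section 4.3 of both SAPs (PREPARE Closed and PREPARE Open) gives death a descriptive role: "Participant deaths will also be tabulated". On missing values, Section 5.2 of both SAPs says: "Our primary and secondary analyses will use multiple imputations to account for missing data". Section 5.4 of both names a complete case analysis as the missing-data sensitivity analysis.

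**The concern.** This sentence is an operative instruction. It tells site staff what to ask for when a participant is leaving and the scope of any new permission is being settled. It names an item that is not a trial outcome and calls it the primary one.

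The request matters because permission to learn whether someone is alive is not permission to read the records from which an SSI is classified. The protocol's Study Summary says that outcomes are adjudicated from clinical notes and radiographs. A site that asks for survival status alone may therefore have nothing to send to the Adjudication Committee.

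An outcome lost this way falls to multiple imputation. Protocol 5.2.1 assumes that data are missing at random, and Protocol 5.2.4 concedes that this cannot be verified. Protocol 5.2.4 also offered a worst-case approach to missing outcomes, but it is not among the four sensitivity analyses in either SAP. Complete case is the only missing-data check prespecified there, and it does not test missingness that depends on the outcome. Observing the outcome is better protection than any of these analyses.

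**Working it through.** The main check is a comparison of the texts. Arithmetic serves only to bound the size, because the plan gives no revocation rate and no figure of its own to reproduce.

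**Step 1: item and timing.**

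| | Item | Time point |
|---|---|---|
| Protocol 7.3, request after revocation | Vital status, labelled as primary outcome data | End of scheduled study period (12 months from fracture, by 7.2) |
| Protocol 4.8.1, primary outcome | SSI | 30 days (superficial) or 90 days (deep or organ/space) after definitive surgery |
| Protocol 4.8.2, secondary outcome | Unplanned fracture-related reoperation | 12 months from fracture |
| SAPs 4.3, death | Tabulated only | Not stated |

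The item in 7.3 matches neither outcome. Its time point matches the secondary window but not the primary one. The sentence can be read in two ways. If vital status governs, the site asks about survival. If the words in brackets govern, the site asks about SSI. Neither reading clearly covers reoperation.

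**Step 2: who is exposed.** Data collected before revocation are kept. An SSI already recorded therefore counts, and a participant whose SSI window has closed with status recorded has a complete primary outcome. For SSI, exposure is limited to participants who revoke before the window closes with no event recorded. For reoperation the window runs to 12 months, so retained data protect less: anyone who revokes earlier without a recorded reoperation is exposed.

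**Step 3: upper bound on SSIs touched.** Inputs: N = 6,280 closed and 1,540 open; chlorhexidine-arm risks of 3.5% and 12.5% (Protocol 5.1); risk ratio 0.65 (Protocol Tables 5 and 6). Assumptions: 1–3% revoke; every one of them loses SSI status; their risk equals the average of the two arms.

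- Average risk, closed: (3.5% + 0.65 × 3.5%) / 2 = (3.5% + 2.275%) / 2 = 2.8875%.
- Average risk, open: (12.5% + 8.125%) / 2 = 10.3125%.
- Expected SSIs = N × average risk: 6,280 × 0.028875 = 181.3 closed; 1,540 × 0.103125 = 158.8 open.
- SSIs among revokers = rate × N × average risk:

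| | 1% revoke | 3% revoke |
|---|---|---|
| Closed | 62.8 people, 1.8 SSIs | 188.4 people, 5.4 SSIs |
| Open | 15.4 people, 1.6 SSIs | 46.2 people, 4.8 SSIs |

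On this common base the share of events equals the share of people, 1–3%. Step 2 makes it an upper bound, since some revokers will already have SSI status recorded.

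**Step 4: effect on power.** Two-proportion normal approximation, two-sided 5%, n per arm, clustering and all other loss ignored:

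power = Φ{ [|p₁ − p₂|√n − 1.96√(2p̄(1 − p̄))] / √(p₁(1 − p₁) + p₂(1 − p₂)) }

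| SSI status lost | Open (N 1,540) | Closed (N 6,280) |
|---|---|---|
| 0% | 80.6% | 82.6% |
| 1% | 80.3% | 82.2% |
| 2% | 79.9% | 81.9% |
| 5% | 78.6% | 80.7% |

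These figures show scale only; the protocol's own power came from simulation. The loss is below one percentage point at 1–2% and about two points at 5%.

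**The case against.** The strongest reply is that this is a labelling slip. The sentence sets a floor, and the words in brackets ask for primary outcome data, which the protocol consistently defines as SSI. A sensible coordinator would ask about infection. Site instructions or forms outside these documents may also name SSI. The sample size already allows for 10% loss to follow-up, and nothing in the documents links revocation to complications or to the solution used.

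Much of this stands, and it rules out three stronger conclusions that a reader might draw:

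- *That sites are told to seek vital status and nothing more, so SSI is not obtained.* The text sets a minimum, and nowhere does the plan say that SSI will not be sought after revocation.
- *That every revoking participant's outcomes become missing and must be imputed.* The retention rule in the same paragraph of 7.3 contradicts this.
- *That up to about 4% of events are at stake.* This comes from mixing bases. It takes 3% of all enrolled at the chlorhexidine-arm risk (188 × 3.5% = 6.6; 46 × 12.5% = 5.8) and divides by events expected in both arms after 10% loss (2,826 × 0.05775 = 163; 693 × 0.20625 = 143). On one base the figure is 3%.

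The reply does not rescue the sentence. A rule that can be met in full without asking about either outcome, and that sites may read in different ways, does not do its job.

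**Conclusion.** Wrong as written, with a small effect. Protocol 7.3 equates vital status with the primary outcome, and the protocol's own definitions contradict that. The consequence is possible avoidable missing data in participants who revoke before an outcome window closes with no event recorded. It is not a certain loss in all who revoke.

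At an assumed 1–3% revocation rate, at most 1–3% of expected SSIs are touched. That bound rests on the assumed rate and on revokers having average planning risk. If they had more complications than average, the share would rise in proportion; a link is plausible in an open-label trial, but the documents do not show one. The case for correction is that the missingness is avoidable and that the SAPs prespecify no analysis of outcome-related missingness. The loss of power is minor.

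**What to change.** In Protocol 7.3, replace the phrase on vital status with a minimum request that names three items:

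1. SSI status through the 30- and 90-day windows after definitive fracture management surgery (primary outcome);
2. unplanned fracture-related reoperation to 12 months from fracture (secondary outcome);
3. vital status.

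State that these are collected by record review or contact, as far as the participant's new permission allows. Record review is already a data source under Protocol 4.8.4, but after revocation it needs that permission.

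The cost is one sentence in the protocol and the matching site instruction, with no added visits. Whether it is an administrative clarification or a formal amendment is decided under Protocol 7.4.

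If data collection is already complete, report by arm how many participants revoked before their SSI window closed with no event recorded, how many revoked before 12 months with no reoperation recorded, and what was requested from them.

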7.4 Protocol Amendments

Any amendments to the study protocol which will affect the conduct of the study, impact the safety or benefits to participants or affect the analysis and the interpretation of the safety and efficacy of the intervention under investigation (e.g., changes to the study objectives, study design, sample size, or study procedures) will necessitate a formal amendment to the protocol. Any protocol amendments will be approved by the Principal Investigators and will require approval by the McMaster University REB, the Central IRB, local IRBs/REBs, as well as the Funder (as needed). The Methods Center will also file an amendment to all applicable regulatory agencies for changes to the protocol made after the original regulatory approval. Clinical sites will also be required to submit amendment requests to their IRB of Record to obtain approval for the amendment and to provide the Methods Center with a copy of this approval. Administrative changes (e.g., minor corrections or clarifications that have no effect on the way the study is conducted) will not need to undergo a formal amendment process.

7.5 Adverse Event Reporting and Definitions

7.5.1 Serious Adverse Event (SAE)

A SAE is any adverse event that is any of the following:

- Fatal
- Life threatening
- Requires or prolongs hospital stay

- Results in persistent or significant disability or incapacity
- A congenital anomaly or birth defect
- An important medical event

7.5.2 Unanticipated Problems Resulting in Risk to Participant or Others

Any incident, experience, or outcome that meets the following criteria:

- Unexpected in nature, severity, or frequency (e.g., not described in study-related documents such as the ethics-approved protocol or consent form, etc.).
- Related or possibly related to participation in the research (i.e., possibly related means there is reasonable possibility that the incident experience or outcome may have been caused by the procedures involved in the research).
- Suggests that the research places participants or others at greater risk of harm (including physical, psychological, economic, or social harm).

